Appendix 16.2.1.8 ATI-50002 Application Changes and Missed Doses

Patient	Application Frequency Started	Study Day ^a Dispensed	Application Frequency Ended	Study Day ^a Collected	Applications/Day
XX-XXX	ddmmmyyyy	XX	ddmmmyyyy	XX	XX
	ddmmmyyyy	XX	ddmmmyyyy	XX	XX
	ddmmmyyyy	XX	ddmmmyyyy	XX	XX
	ddmmmyyyy	XX	ddmmmyyyy	XX	XX
	ddmmmyyyy	XX	ddmmmyyyy	XX	XX
	ddmmmyyyy	XX	ddmmmyyyy	XX	XX
	ddmmmyyyy	XX	ddmmmyyyy	XX	XX
	ddmmmyyyy	XX	ddmmmyyyy	XX	XX
	ddmmmyyyy	XX	ddmmmyyyy	XX	XX

^a Dispensed Date (or Collection Date) – Date first Application +1.

23 Apr 2019 Statistical Analysis Plan

Protocol: ATI-50002-AGA-201

Appendix 16.2.1.9

Group: Female, Male

Patient	Inclusion Criteria Not Met	Exclusion Criteria Not Met
	1,213	None
	None	1,216

Eligibility Criteria

Aclaris Therapeutics Inc.	23 Apr 2019
Protocol: ATI-50002-AGA-201	Statistical Analysis Plan

Appendix 16.2.1.10 Protocol Violations

Group: Fe	male, Male			
Patient	Violation			

23 Apr 2019 Statistical Analysis Plan

Appendix 16.2.2.1
Target Area Hair Count and Width

Group: Fem	Group: Female, Male						
Patient	Visit	Assessment Date	Study Day ^a	TAHC (hairs/cm²)	TAHW (cm)		
xx-xxx	V2 – Day 1	ddmmmyyyy	XX	xxx	xxx		
	V5 – Week 8	ddmmmyyyy	XX	XXX	XXX		
	V7 – Week 16	ddmmmyyyy	XX	XXX	XXX		
	V10 – Week 26	ddmmmyyyy	XX	XXX	XXX		
	V16 – Week 52	ddmmmyyyy	XX	XXX	XXX		

^a Assessment date – date of first application of study medication (+1 if ≥ first application of study medication).

23 Apr 2019 Statistical Analysis Plan

Protocol: ATI-50002-AGA-201

Appendix 16.2.2.2 Investigator and Subject Global Assessments

Patient	Visit	Assessment Date	Study Day ^a	Investigator Global Assessment ^b	Subject Global Assessment ^t
xx-xxx	V5 – Week 8	ddmmmyyyy	XX	-3	-3
AA AAA	V7 – Week 16	ddmmmyyyy	XX	-2	-2
	V10 – Week 26	ddmmmyyyy	XX	-1	-1
	V13 – Week 39	ddmmmyyyy	XX	0	0
	V16 – Week 52	ddmmmyyyy	XX	1	1
	Early Term 1st 26 Weeks	ddmmmyyyy	XX	2	2
	Follow-Up 1st 26 Weeks	3333		3	3
	Early Term 6 Month Extension				
	Follow-Up 6 Month Extension				

Programming note: Differentiation between Early term and Follow-up is based on the availability of V10 (1st 26 Weeks) or V16 (patients entering extension) data for ANY data (not just global assessments). If a patient does not enter the extension and had no data collected for V10 and had discontinued the trial the follow-up is considered "Early Term 1st 26 Weeks". If they had V10 and did not enter the extension then it's "Follow-Up 6 Month Extension". Similarly for those entering extension, those without a V16 who discontinued the study are assigned "Early Term 6 Month Extension" and those with V16 are assigned to "Follow-Up 6 Month Extension".

^a Assessment date – date of first application of study medication (+1 if ≥ first application of study medication).

b -3: Greatly decreased hair growth; -2: Moderately decreased hair growth; -1: Slightly decreased hair growth; 0: No Change; +1: Slightly increased hair growth; +2: Moderately increased hair growth; +3: Greatly increased hair growth.

Appendix 16.2.2.3 Norwood-Hamilton Scale in Males

Patient	Visit	Assessment Date	Study Day ^a	N-H Score	Improvement from Baseline (Yes/No) ^c
VV VVV	V1 Caraanina	ddmmmraaa	WW	I	Yes/No
XX-XXX	V1 - Screening V2 – Day 1	ddmmmyyyy	XX XX	Π_{p}	I ES/INO
	V2 – Day 1 V7 – Week 16	ddmmmyyyy ddmmmyyyy	XX	II IIa	
	V10 – Week 16 V10 – Week 26	ddmmmyyyy		IIa III	
	V16 – Week 20 V16 – Week 52		XX	IIIa	
		ddmmmyyyy	XX		
	Early Term 1 st 26 Weeks Follow-Up 1 st 26 Weeks	ddmmmyyyy	XX	III Vertex IV	
	*			IV IVa	
	Early Term 6 Month Extension			Iva V	
	Follow-Up 6 Month Extension			·	
				Va VI	
				VI VII	

^a Assessment date – date of first application of study medication (+1 if ≥ first application of study medication).

Programming note: Differentiation between Early term and Follow-up is based on the availability of V10 (1st 26 Weeks) or V16 (patients entering extension) data for ANY data (not just Norwood-Hamilton). If a patient does not enter the extension and had no data collected for V10 and had discontinued the trial the follow-up is considered "Early Term 1st 26 Weeks". If they had V10 and did not enter the extension then it's "Follow-Up 1st 26 Weeks". Similarly for those entering extension, those without a V16 who discontinued the study are assigned "Early Term 6 Month Extension" and those with V16 are assigned to "Follow-Up 6 Month Extension".

^b Used as baseline for analysis.

^c Yes – score improved by ≥1 level including shifts in "sub-level" (e.g. IIIa to III is considered a 1 level improvement).

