### **6.2. Secondary Objectives**

The secondary objectives will assess the following:

- development of new hair growth/scalp coverage as assessed by the investigator and the subject using a seven-point rating scale and global scalp photographs.
- to assess the change from baseline in cumulative target area hair width (TAHW)
- assess the change in AGA stage according to the Norwood Hamilton scale in males and the Sinclair Scale in females.

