## **8. SELECTION AND WITHDRAWAL OF SUBJECTS**

### **8.1. Subject Inclusion Criteria**

Subjects must meet the following criteria to be eligible for participation in the study:

1. Able to comprehend and willing to sign an Informed Consent Form (ICF).
2. Male subjects and non-pregnant, non-nursing female subjects 18 to 50 years of age with a clinical diagnosis of AGA.
3. Male subjects with a Norwood-Hamilton classified as III vertex, IV or V and woman subjects with a Sinclair Grade 2, 3 or 4.
4. Subjects willing to agree to have small 1.9 cm diameter circle of hair clipped to ~ 1 mm in length on their balding scalp.
5. Subjects willing to agree to have a permanent dot tattoo applied to their scalp to mark the center of the identified target area.
6. Subjects must agree to maintain the same hair style and hair care regimen during the study.
7. Subjects must agree to not use a medicated shampoo or conditioner containing biotin, saw palmetto or tea tree oil (melaleuca oil) throughout the course of protocol treatment and refrain from hair weaving, hair extensions, texturizers, relaxers, occlusive wigs and non-study hair growth products during the study and for a period of 30 days prior to Visit 2.
8. Subjects must have an absolute neutrophil count (ANC)  $>1,000/\text{mm}^3$ , and a platelet count  $>50,000/\text{mL}$ .
9. Male subjects with a serum prostate-specific antigen (PSA) level of  $<2.0 \text{ ng/mL}$ .
10. Subjects receiving oral or topical hormones must be on a stable dose for 6 months prior to Visit 2.
11. Subjects must be willing to refrain from washing hair, using hair products, and participating in strenuous exercise that would cause profuse sweating for 6 hours after each treatment application with ATI-50002.
12. Woman of child bearing potential (WOCBP) must agree to use an approved method of highly effective birth control for the duration of the study and for 30 days after last study medication application.
13. Sexually active male subjects must agree to use a barrier form of birth control from the first application until 30 days post last application of ATI-50002.

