### **13.3. Secondary Efficacy Endpoints**

Mean change from baseline in cumulative TAHW will be quantified using a microphotographic technique and calculated along with the median, standard deviation, standard error, and 95% confidence limits around each mean change to allow tests of the null hypothesis that the population mean changes are zero.

The seven-point rating scale to measure the investigator and subject assessment of the development of new hair growth/scalp coverage will be analyzed with summary statistics (N, mean, median, SD) for each visit where the assessment is made. Similar summary statistics will be used to analyze change from baseline in AGA stage separately for males (Horwood Hamilton Scale) and for females (Sinclair Scale) at each applicable visit.

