## APPENDIX 2. NORWOOD HAMILTON SCALE

(Gupta M and Mysor V, 2016)

Type I: Minimal or no recession of the hairline

Type II: Triangular, usually symmetrical, areas of recession at the frontotemporal hairline

Type III: Deep symmetrical recession at the temples that are bare or only sparsely covered by hair. In Type III vertex, the hair loss is primarily from the vertex with limited recession of the frontotemporal hairline that does not exceed the degree of recession seen in Type III.

[figure not shown]
Type IV: Frontotemporal recession is more severe than in Type III and there is sparse hair or no hair on the vertex. The two areas of hair loss are separated by a band of moderately dense hair that extends across the top. The is band connects with the fully haired fringe on the sides of the scalp.

Type V: The vertex hair loss region is still separated from the frontotemporal region but it is less distinct. The band of hair across the crown is narrower and sparser and the vertex and frontotemporal regions of hair loss are bigger.

Type VI: The bridge of hair that crosses the crown is gone with only sparse hair remaining. The frontotemporal and vertex regions are joined together and the extent of hair loss is greater.

Type VII: The most severe form of hair loss and only a narrow band of hair in a horseshoe shape remains on the sides and back of the scalp. This hair is usually not dense and may be quite fine.

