^a The number of patents with an assessement at the visit. Used as denominator for percentages.

Table 14.2.4
Improvement from Baseline in Norwood-Hamilton Scale in Males
ITT Population

Visit	=	Improved by ≥ 1 Level	Improved by ≥ 2 Levels	
Shift Detail ^a	N^b	n (%)	n (%)	
V7 – Week 16	XX	xx (xx.x)	xx(xx.x)	
IV – IIIa		xx (xx.x)	xx (xx.x)	
IV – III vertex		xx (xx.x)		
etc				
V10 – Week 26	XX	xx (xx.x)	xx (xx.x)	
IV – IIIa		xx (xx.x)	xx (xx.x)	
IV – III vertex		xx (xx.x)		
etc				
V16 – Week 52	XX	xx (xx.x)	xx (xx.x)	
IV – IIIa		xx (xx.x)	xx (xx.x)	
IV – III vertex		xx (xx.x)	, ,	
etc		` '		
FU/Early Termination ^c	XX	xx (xx.x)	xx (xx.x)	
IV – IIIa		xx (xx.x)	xx (xx.x)	
IV – III vertex		xx (xx.x)	,	
etc		,		
Early Term, 1st 26 Weeks	XX	xx (xx.x)	xx (xx.x)	
IV – IIIa		xx (xx.x)	xx (xx.x)	
IV – III vertex		xx (xx.x)	9	
etc		ini (mini)		

 $^{^{}a}$ The Baseline Score →Timepoint Score combination that met the ≥ 1 level improvement criteria.

^b The number of patients with a non-missing score baseline and at the visit indicated. Used as denominator for percentages.

^c Includes early terminations or follow-ups collected during the first 26 Weeks or during the additional six months for patients opting to continue treatment in the optional six month extension. Additional rows provided to further sub-divide based on the period (1st 26 Weeks vs 6 Month Extension) and termination status (early termination vs follow-up).

Protocol: ATI-50002-AGA-201

Table 14.2.4
Improvement from Baseline in Norwood-Hamilton Scale in Males
ITT Population

Visit Shift Detail ^a	N^b	Improved by ≥ 1 Level n (%)	Improved by ≥ 2 Levels n (%)	
E II 4st AC W		(()	
Follow-Up 1st 26 Weeks	XX	xx (xx.x)	xx(xx.x)	
IV – IIIa		xx (xx.x)	xx(xx.x)	
IV – III vertex		xx (xx.x)		
etc				
Early Term, 6 Month Extension	XX	xx (xx.x)	xx (xx.x)	
IV – IIIa		xx (xx.x)	xx (xx.x)	
IV – III vertex		xx (xx.x)		
etc				
Follow-Up, 6 Month Extension	XX	xx (xx.x)	xx (xx.x)	
IV – IIIa		xx (xx.x)	xx (xx.x)	
IV – III vertex		xx (xx.x)		
etc				

^a The Baseline Score → Timepoint Score combination that met the ≥ 1 level improvement criteria.

PROGRAMMING NOTE: Add rows for each combination that shows an improvement starting from greatest improvement and highest baseline score.

^b The number of patients with a non-missing score baseline and at the visit indicated. Used as denominator for percentages.

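### The SAP counts Norwood-Hamilton sub-types as full levels, so a one-type change such as IV to IIIa is shown as improvement by two or more levels; the Sinclair shell also misplaces its shifts

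*SAP*

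**What the plan says.** **Protocol.** Section 6.2 makes it a secondary objective to "assess the change in AGA stage according to the Norwood Hamilton scale in males", with the Sinclair scale for women. Section 13.3 plans the analysis: "Similar summary statistics will be used to analyze change from baseline in AGA stage separately for males" and for females, meaning N, mean, median and SD by visit. It defines no level-based responder. Section 8.1 admits "Male subjects with a Norwood-Hamilton classified as III vertex, IV or V". The text of Appendix 2 describes Types I to VII and places III vertex within the Type III entry. It names no a-variants. Appendix 3 gives Sinclair grades 1 to 5.

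**SAP, men.** Appendix 16.2.2.3 lists 12 possible scores: I, II, IIa, III, IIIa, III Vertex, IV, IVa, V, Va, VI, VII. Footnote c sets the improvement flag to Yes when the "score improved by ≥1 level including shifts in" sub-level, and gives the example "e.g. IIIa to III is considered a 1 level improvement". Table 14.2.4 has two outcome columns, one for at least one level and one headed "Improved by ≥ 2 Levels", with a row for each baseline-to-visit combination that improved. In the shell, IV to IIIa is filled in both columns and IV to III vertex only in the first.

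**SAP, women.** Table 14.2.5 uses the same two columns. The row 4 to 3 is filled in both. The row 3 to 2 and, in the later blocks, the row 4 to 2 are filled only in the first.

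**The concern.** A reader of a column for two or more levels will take it to mean a large change in stage. If sub-types are levels, a man who moves by a single Norwood type can land there, and so can a man whose loss is relabelled within Type III.

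Change in stage is a named secondary endpoint, and Tables 14.2.4 and 14.2.5 are its only summaries among the SAP shells available. The treating investigator rates the scale (Protocol 11.2) in an open-label study with no control arm. The blinding in Protocol 11.1 and Appendix 5 covers the hair-image analysis, not this rating. A rule that turns small relabellings into levels therefore has nothing to offset it.

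The Sinclair shell raises a simpler problem: followed literally, it would report a one-grade shift as two and a two-grade shift as one.

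**Working it through.** **Inputs.** The 12 scores in the order of SAP Appendix 16.2.2.3, ranked I = 1, II = 2, IIa = 3, III = 4, IIIa = 5, III vertex = 6, IV = 7, IVa = 8, V = 9, Va = 10, VI = 11, VII = 12. Eligible male baselines III vertex, IV and V (Protocol 8.1). Twelve men (Protocol 7.2).

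**Formulas.** SAP levels improved = baseline rank − visit rank. Whole types improved = baseline Roman numeral − visit Roman numeral, with III, IIIa and III vertex all counted as 3, and IV and IVa as 4.

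**The SAP's own examples first, then other shifts.**

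| Shift | SAP list steps | Whole types | Source of the SAP count |
|---|---|---|---|
| IIIa to III | 5 − 4 = 1 | 0 | stated, footnote c |
| IV to III vertex | 7 − 6 = 1 | 1 | Table 14.2.4 shell |
| IV to IIIa | 7 − 5 = 2 | 1 | Table 14.2.4 shell |
| V to IVa | 9 − 8 = 1 | 1 | inferred from list order |
| V to IV | 9 − 7 = 2 | 1 | inferred |
| IV to III | 7 − 4 = 3 | 1 | inferred |
| III vertex to III | 6 − 4 = 2 | 0 | inferred |
| III vertex to II | 6 − 2 = 4 | 1 | inferred |

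The ranking reproduces all three SAP examples.

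**How many shifts are affected.** A score reaches two or more SAP levels if its rank is at least 2 below baseline. From III vertex (rank 6) that is 4 scores, from IV (rank 7) 5 scores, and from V (rank 9) 7 scores: 4 + 5 + 7 = 16 shifts. Six of these are a drop of one type or none: III vertex to III, IIa or II; IV to IIIa or III; V to IV. The other 10 are drops of two or more types under either count. Counted in whole types, none of the six reaches two levels: III vertex to III scores 0 and the other five score 1.

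**Size per man.** 100 / 12 = 8.3 percentage points for each man moved into or out of a column. Table 14.2.4 uses men with a score at baseline and at the visit as its denominator, so the step grows if fewer are assessed.

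**Sinclair.** 4 − 3 = 1 grade, but the shell fills both columns. 4 − 2 = 2 grades, but the shell fills only the first. 3 − 2 = 1 grade, correctly in the first column only.

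**The case against.** The strongest reply has four parts.

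**The two-level rule is not written.** Footnote c defines only a Yes/No flag for at least one level. The shell cells are placeholders, and the Sinclair cells show that they can be wrong. This stands: the cells alone are weak evidence, and it would be too much to say that the SAP states V to IV as two levels. What carries the point is that the footnote, the list order and the male cells all agree. The lack of a written rule is itself a reason to supply one.

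**The scale is the same.** A reader might infer that the SAP uses a scale that the protocol does not. The documents do not support that. The protocol names Norwood-Hamilton throughout, and the Appendix 2 figure is not available here. All that can be said is that the Appendix 2 text does not define the a-variants.

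**The order may be sensible.** Appendix 2 says "In Type III vertex, the hair loss is primarily from the vertex with limited recession of the frontotemporal hairline", and for the next stage "Type IV: Frontotemporal recession is more severe than in Type III and there is sparse hair or no hair on the vertex". Placing III vertex between III and IV fits that description, so it is not shown that the list is out of severity order. Scoring III vertex to III as no level is also debatable, since a man could regain vertex hair and remain Type III. This stands, and is why such shifts should stay visible in their own rows.

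**Nothing is hidden.** Table 14.2.4 prints each improving combination and the listing gives every score, so a reader can recount. This is true and limits the harm, but the column totals will be what is quoted.

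**Conclusion.** The point holds as a correction to a secondary, descriptive summary. Footnote c counts sub-types as full levels, and the male shell consequently places a one-type change (IV to IIIa) under two or more levels. By list order the same happens to V to IV and IV to III, and III vertex to III scores two levels with no change of type. Those last three rest on the assumption that each neighbouring entry in the list is one level, which no rule in the SAP text available states.

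Not every one-type change is inflated: IV to III vertex and V to IVa each score one level. Nor does returning to the entries in Protocol Appendix 2 settle the matter. If III and III vertex are separate steps, IV to III is still two, so a level has to be defined in either case.

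The Sinclair misplacement needs no assumption beyond the five-grade scale.

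Each reclassified man moves a rate by 8.3 percentage points if 12 are assessed. The number of men affected cannot be known from the plan. The primary endpoint, change in non-vellus target area hair count, is not touched.

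**What to change.** **Footnote c and Table 14.2.4.** Define a level as a change of whole Norwood type (I to VII), and write the rules for one and for two levels explicitly. Move IV to IIIa to the first column only. Show within-type shifts (a-variants, and III vertex to or from III or IIIa) in separate rows that count toward neither column, so that a vertex improvement within Type III remains visible.

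**Table 14.2.5.** Put one-grade shifts (4 to 3, 3 to 2, 2 to 1) in the first column only, and shifts of two or more grades (4 to 2, 3 to 1, 4 to 1) in both. List 4 to 2 above 4 to 3, as the table's own note on row order requires.

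**Cost.** SAP wording, two shells and one derivation, with no new data. The downside is that fewer men will be counted as improved, including any whose only change is within a type.

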Appendix 16.2.2.4 Sinclair Scale in Females

Patient	Visit	Assessment Date	Study Day ^a	Sinclair Score	Improvement from Baseline (Yes/No)
xx-xxx	V1 - Screening	ddmmmyyyy	XX	1	Yes/No
	V2 – Day 1	ddmmmyyyy	XX	2 ^b	
	V7 – Week 16	ddmmmyyyy	XX	3	
	V10 – Week 26	ddmmmyyyy	XX	4	
	V16 – Week 52	ddmmmyyyy	XX	5	
	Early Term 1 st 26 Weeks Follow-Up 1 st 26 Weeks Early Term 6 Month Extension Follow-Up 6 Month Extension	ddmmmyyyy	XX		

Programming note: Differentiation between Early term and Follow-up is based on the availability of V10 (1st 26 Weeks) or V16 (patients entering extension) data for ANY data (not just Sinclair score). If a patient does not enter the extension and had no data collected for V10 and had discontinued the trial the follow-up is considered "Early Term 1st 26 Weeks". If they had V10 and did not enter the extension then it's "Follow-Up 1st 26 Weeks". Similarly for those entering extension, those without a V16 who discontinued the study are assigned "Early Term 6 Month Extension" and those with V16 are assigned to "Follow-Up 6 Month Extension".

^a Assessment date – date of first application of study medication (+1 if ≥ first application of study medication).

^b Used as baseline for analysis.

23 Apr 2019 Statistical Analysis Plan Protocol: ATI-50002-AGA-201

Appendix 16.2.3.1 All Adverse Events

Group: Female, Male

Patient	MedDRA SOC/ MedDRA Preferred Term/ CRF Verbatim Term (AE No.)	Onset Study Day ^a Resolution Study Day ^b Duration (Days) ^c	Onset Date/ Stop Date Cutaneous AE?	Relationship/ Action Taken/ Therapy Required	Serious/ Severity/ Outcome
501-01	Cardiovascular System /	62	01Sep12	Related	Yes/No
	Bradycardia /	64		Not Related	
	Slow Heart Rate (xx) ^d	3	03Sep12		Mild/Moderate/Severe
			Ongoing	Dose not changed	
			0 0	Dose Reduced	Recoverd/Resolved
			Yes (Scalp),	Dose Interrupted	Not Recovered/Resolved
			Yes (not Scalp),	Drug Withdrawn	Recovered/Resolved w/ Seq.
			No	Unknown	Fatal Unknown
				Yes/No	

^a AE onset date – date of first application of study medication (+1 if ≥ first application).

PROGRAMMING NOTES: Sort by group, patient, onset date, SOC and PREF term. Display partial dates as entered in raw data. Use derived dates for study day and duration

Appendix 16.2.3.2 Serious Adverse Events

Adverse Events Resulting in Discontinuation of Study Treatment Appendix 16.2.3.3

Appendix 16.2.3.4 Adverse Events Resulting in Outcome of Death

^b AE resolution date – date of first application of study medication (+1 if ≥ first application).

^c Resolution Date – Onset Date +1

^d Not treatment emergent = Onset either prior to the first application or > 30 days after the last application of study medication.

23 Apr 2019 Statistical Analysis Plan

Protocol: ATI-50002-AGA-201

Appendix 16.2.3.5 Local Skin Reactions

Patient	Visit	Assessment Date	Study Day ^a	Assessor	Sign ^b	Grade
	V2 – Day 1	ddmmmyyyy	1	Investigator	Erythema	1
	•			-	Scaling	2
					Dryness	3
				Subject	Stinging/burning	
				•	Itching	
				Investigator	NO SIGN GRADED >0	
				Subject/Legal Guardian	NO SIGN GRADED >0	
	V3 – Week 3	ddmmmyyyy	21			

^a Assessment Date – Date first Application +1.

^b Only signs with grade > 0 are displayed. Within assessor, if all signs were grade 0 (or not done) appear as "NO SIGN GRADED > 0".

23 Apr 2019 Statistical Analysis Plan

Protocol: ATI-50002-AGA-201

Appendix 16.2.3.6 Physical Exam

Group: Female, Male

Patient	Assessment Date	Visit	Study Day ^a	Body System	Finding ^b	Description of Finding
xx-xxx	ddmmmyyyy	V1 – Screening ET/Follow-Up	XX		Normal, no findings	
		1		Body System a Body System b	Abnormal, CS Abnormal, NCS	XXXXXXXXXXXXXXXXXXXXXXXXXXXXXXXXXXXXXX

NOTE: Listing includes only lists body systems that were assessed with Abnormalities. Patients with only "normal" findings are listed as "Normal, no findings" (can have some body systems "not done" so long as those that were assessed are all "normal". Not done are not listed.)

^a Assessment Date – Date of First Application (+1 if ≥ first application of study medication).

^b CS = Clinically Significant; NCS = Not Clinically Significant

23 Apr 2019 Statistical Analysis Plan

Protocol: ATI-50002-AGA-201

